1144 Fasted (≥ 8 h) blood draws, and post-exercise blood draws will be collected as outlined below to
1145 assess fractional iron absorption and relevant biomarkers of inflammation, muscle damage,
1146 appetite, and nutritional and metabolic stress responses to SUSOPS (**Tables 1**). A total of 42
1147 blood draws (≤ ~530 mL) will be collected during the entire study.

1148

1149 **Table 1.** Blood sample collection per analyte¹

	SUSOPS 1					Recovery 1				SUSOPS 2				Recovery 2			
Days	2	3	4	5	6	7	8	9	12	13	14	15	16	17	18	19	22
Tracer/tracee ²	7	x	x	x	7	x	x	x	x	x	x	x	7	x	x	x	x
Hgb/Hct	x	x	x	x	x	x	x	x	x	x	x	x	x	x	x	x	x
Erythroferrone ²	7	x	x	x	7	x	x	x	x	x	x	x	7	x	x	x	x
c-myomiRNA		x		x	x					x		x	x				
Exo miRNA		x		x	x					x		x	x				

Ferritin ²	7	x	x	x	7	x	x	x	x	x	x	x	7	x	x	x	x
sTfR	x	x	x	x	x	x	x	x	x	x	x	x	x	x	x	x	x
Hepcidin ²	7	x	x	x	7	x	x	x	x	x	x	x	7	x	x	x	x
Iron ²	7	x	x	x	7	x	x	x	x	x	x	x	7	x	x	x	x
TIBC	x	x	x	x	x	x	x	x	x	x	x	x	x	x	x	x	x
IL-6 ²	7	x	x	x	7	x	x	x	x	x	x	x	7	x	x	x	x
hs-CRP	x	x	x	x	x	x	x	x	x	x	x	x	x	x	x	x	x
Erythropoietin		x			x					x			x				
Cortisol		x		x		x		x	x	x		x		x		x	x
CK		x		x		x		x	x	x		x		x		x	x
LDH		x		x		x		x	x	x		x		x		x	x
Myoglobin		x		x		x		x	x	x		x		x		x	x
T-test		x		x		x		x	x	x		x		x		x	x
SHBG		x		x		x		x	x	x		x		x		x	x
LH		x		x		x		x	x	x		x		x		x	x
DHEA-S		x		x		x		x	x	x		x		x		x	x
Insulin ³		2		2		x		x	x	2		2		x		x	x
FFA ³		2		2		x		x	x	2		2		x		x	x
Glycerol ³		2		2		x		x	x	2		2		x		x	x
Glucose ³		2		2		x		x	x	2		2		x		x	x
β-HB ³		2		2		x		x	x	2		2		x		x	x
Osmolality	x	x	x	x	x	x	x	x	x	x	x	x	x	x	x	x	x
Leptin ³		x		x		x		x		x		x		x		x	
Acyl ghrelin ³		2		2		x		x		2		2		x		x	
PYY ³		2		2		x		x		2		2		x		x	
GLP-1 ³		2		2		x		x		2		2		x		x	
PP ³		2		2		x		x		2		2		x		x	
I-FABP ³		2		2						2		2					
Zonulin ³		2		2				x		2		2				x	
LBP ³		2		2				x		2		2				x	
S100B ³		2		2				x		2		2				x	
Ex vivo PBMC	x				x								x				
Serum archive ⁴	8	2	x	2	8	x	x	x	x	2	x	2	8	x		x	x
EDTA archive ⁴	x	2	x	2	x	x	x	x	x	2	x	2	x	x		x	x
LiHep archive ⁴	x	2	x	2	x	x	x	x	x	2	x	2	x	x		x	x
mRNA-seq	x				x			x					x			x	
Metabolomics	x				x			x					x			x	

1150 ¹Analyte abbreviations: Hbg/Hct, hemoglobin/hematocrit; c-myoMIR, circulating muscle-specific
1151 microRNA; sTfR, soluble transferrin receptor; T-saturation, transferrin saturation; TIBC, total iron binding
1152 capacity; IL-6, interleukin-6; hs-CRP, high-sensitivity C-reactive protein; CK, creatine kinase; LDH, lactate
1153 dehydrogenase; T-test; total testosterone; SHBG, sex-hormone binding globulin; LH, luteinizing
1154 hormo33.5.ne; DHEA-S, dehydroepiandrosterone-sulfate; FFA, free-fatty acids; β-HB, beta-
1155 hydroxybutyrate; GLP-1, glucagon-like peptide-1; PYY, peptide-YY; PP, pancreatic polypeptide; I-FABP,
1156 intestinal fatty acid binding protein; LBP, lipopolysaccharide binding protein, PBMC, peripheral blood
1157 mononuclear cells. ²Blood will be sampled seven times during the fractional iron absorption studies
1158 through an indwelling venous catheter for the notated analytes (0, 20, 40, 60, 120, 240, and 360 min) for
1159 a total of 21 blood draws (seven per iron study). A final blood draw will be taken on each of the iron study
1160 mornings (1 per iron study morning; 3 total) through the indwelling venous catheter that is separate from
1161 the seven draws for the iron studies in order to analyze the remaining markers (marked with an x on days
1162 2, 6, and 16) at the same time of day as those measured on the other study mornings when blood draws

1163 occur after an overnight fast (venipuncture). ³A second blood sample will be collected post-exercise for
1164 the notated analytes on days 3, 5, 13, and 15. ⁴Serum, EDTA, LiHep archived blood samples are derived
1165 from the blood draws at each specific time point, and stored in the event certain assays require re-
1166 analysis, or for future analysis if any sample remains. Based on this explanation, the total number of
1167 study blood draws is 42 (iron study days, 8 x 3 = 24; 2 on days 3, 5, 13, and 15, for 8 total draws; and 1
1168 on every other indicated blood draw day, 10 total). Serum and plasma will be archived from each blood
1169 draw. The total volume of blood collected per participant is ≤ ~530 mL.
1170

1171 **Saliva analysis**

1172 Saliva collection is a non-invasive technique with easy achievability that may facilitate sample
1173 collection in austere environments by study volunteers with minimal instruction. The technique
1174 may therefore provide an efficient alternative to using blood and/or fecal collection to monitor
1175 physiological status in Warfighters engaged in SUSOPS or during deployment. However, the
1176 validity of saliva collection as a deployable solution for monitoring physiologic status requires
1177 validation. As such, saliva and blood samples will be collected in tandem. Blood will be
1178 subjected to mRNA-seq, targeted micro-RNA (see *mRNA, myomiR, and c-myomiR Expression*
1179 below) and metabolomics analyses. Saliva will be subjected to microRNA profiling, ion
1180 abundance measurement and metabolomics analyses. Results will be compared between
1181 sample types, and in relation to the gut microbiome, and cognitive and physical performance
1182 outcomes. In addition to validating the approach, analyses will be undertaken to explore
1183 associations between the salivary microbiome and stress responses.
1184

1185 Saliva samples will be collected on study days 2, 6, 9, 16 and 19 at the same time blood
1186 samples will be collected for mRNA-seq, microRNA-seq and metabolomics assays,
1187 respectively. During saliva collection, a Salivette tube with opaque white cap (SARSTEDT, Inc.)
1188 will be opened; the swab will be removed and placed in the mouth. After 45 seconds (gentle
1189 chewing possible, but not required), the saliva-soaked swab will be returned to the Salivette®
1190 which will be closed with the plug for storage and transport. The expected yield is 0.8-1.4 mL
1191 saliva. A second round of sample collection will occur 30 minutes later following the same
1192 procedure. The tubes will be frozen at -80°C and shipped to USACEHR. Upon receiving the
1193 tubes, the tubes will be centrifuged at room temperature at 1000g for 2 minutes. The first tube
1194 will be used for microRNA sequencing and microbiome shot gun sequencing. The second tube
1195 will be used for metabolomics and targeted proteomics (inflammatory panel of 65 protein
1196 markers will be tested using the Luminex platform).
1197

1198 **Determination of Fractional Iron Absorption**

1199 Stable isotope concentrations in whole blood will be determined by inductively coupled plasma
1200 mass spectrometry (ICP-MS) by the Energy and Environmental Sustainability Laboratory
1201 (EESL) at Pennsylvania State University (PSU) using a fee-for-service contract.
1202

1203 The amount of absorbed iron in circulation will be calculated using isotope dilution as described
1204 previously [70, 99]. Briefly, the amount of absorbed iron circulating in blood will be calculated
1205 based on the amount of stable isotope administered, the amount of stable isotope detected in
1206 the blood, hemoglobin concentration, and blood volume, which will be estimated based on
1207 volunteer height and weight [100]. Isotope dilution will also be used to calculate fractional iron
1208 incorporation into red blood cells after administration of the stable isotope and assuming 80%
1209 incorporation [70].
1210

1211 An example calculation using ⁵⁴Fe tracer and endogenous concentrations of ⁵⁶Fe is included
1212 below:
1213

$${}^{54}\text{Fe}_{\text{inc}} = \frac{\left(\frac{{}^{54}\text{Fe}}{{}^{56}\text{Fe}_{\text{enr}}} - \frac{{}^{54}\text{Fe}}{{}^{56}\text{Fe}_{\text{base}}} \right) \text{Fe}_{\text{circ}} \cdot \text{NA}_{54}}{\frac{{}^{54}\text{Fe}}{{}^{56}\text{Fe}_{\text{base}}}}$$

- 1214
1215 ${}^{54}\text{Fe}_{\text{inc}}$ = quantity of ${}^{54}\text{Fe}$ incorporated into red blood cells
1216 ${}^{54}\text{Fe}/{}^{56}\text{Fe}_{\text{enr}}$ = enriched isotope ratio
1217 ${}^{54}\text{Fe}/{}^{56}\text{Fe}_{\text{base}}$ = baseline isotope ratio
1218 Fe_{circ} = total circulating iron
1219 NA_{54} = natural abundance of ${}^{54}\text{Fe}$

1220

1221 **Muscle Glycogen**

- 1222 Approximately 20 mg of muscle from each muscle biopsy will be dehydrated in a freeze dryer.
1223 Samples will then be ground to powder and visible connective tissue will be removed.
1224 Powdered muscle will be placed in 500 μl 2 N HCl. Samples will then be placed in an incubator
1225 for 120 min at 100°C. Following incubation samples will be neutralized with 1500 μl 0.67 N
1226 NaOH. Muscle glycogen will be in solution at this point. Glycogen will be quantified by a
1227 fluorometric assay (Sigma-Aldrich, St. Louis, MO, USA or equivalent). Muscle glycogen will be
1228 quantified to determine the contribution of endogenous carbohydrate availability on inflammation
1229 in response to SUSUPS BAL and NEG BAL.

1230

1231 **mRNA, myomiR, and c-myomiR Expression**

- 1232 Total RNA will be isolated from approximately 25 mg of muscle using a mirVana™ miRNA
1233 isolation kit (Invitrogen, Carlsbad, CA, USA) or equivalent. Quantity and quality of RNA will be
1234 assessed using a Nanodrop ND-1000 spectrophotometer (Nanodrop, Wilmington, DE, USA).
1235 Equal amounts of total RNA will be synthesized into cDNA for analysis of mRNA (iScript™
1236 Advanced cDNA Synthesis Kit; Bio-Rad or equivalent) and a TaqMan® microRNA RT kit
1237 (Applied Biosystems, Foster City, CA, USA) or equivalent. Individual primers will be used to
1238 determine the mRNA expression of known muscle inflammatory, anabolic, proteolytic,
1239 myogenic, and metabolic markers susceptible to stress, to include but not limited to, TNF- α ,
1240 TNF- α R, IL-6, IL-6R, TWEAK, TWEAK-R, REDD1, Atrogin, MuRF-1, MyoD, Myogenin,
1241 Myogenenin, Pax7, PGC-1 α , SIRT1, p53, ACC, and AMPK. microRNA analysis will be
1242 conducted using individual Taqman® probes (Applied Biosystems) or equivalent, assessing
1243 microRNA that may be associated with inflammation and metabolism. This microRNA targets
1244 will include, but not be limited to, miR-1, miR-23a/b, miR-26, miR-29, miR-34a, miR-103, miR-
1245 107, miR-133a/b, miR-146, miR-206, miR-208a, miR-486, and miR-499a.

1246

- 1247 Following identification of skeletal muscle microRNA that had a significant change, Taqman®
1248 probes (Applied Biosystems) or equivalent will be used to assess the expression of these
1249 microRNA in serum to determine their potential use as noninvasive markers of altered
1250 metabolism in response to elevated inflammation during and following SUSOPS. Circulating
1251 miRNA will be extracted from 200 μL serum using miRNeasy Serum/Plasma kit, which allows
1252 for extraction and purification of small (< 200 nucleotides) cell-free RNA (Qiagen, Valencia, CA,
1253 USA or equivalent). To avoid introduction of potentially contaminating material, prior to RNA
1254 extraction serum samples will be centrifuged for 10 min at 4°C to remove cellular debris.
1255 Supernatant will be removed and transferred to a new tube without disturbing the pellet. Due to

1256 the small amount of RNA in the serum, 3.5 μ L of a Spike-In Control (*C. elegans* miR-39; Qiagen
1257 or equivalent) will be added to all samples prior to extraction of RNA to determine the yield of
1258 template recovered. After extraction 3 μ L of serum RNA will reverse transcribed using the
1259 TaqMan[®] microRNA RT kit (Applied Biosystems) or equivalent with miRNA-specific stem-loop
1260 RT primers pooled in 1X-Tris-EDTA (TE) buffer for a final dilution of 0.05X. A pre-amplification
1261 step will be performed after reverse transcription to increase cDNA template using a primer pool
1262 of 20 X Taqman[®] Small RNA Assays (Applied Biosystems) or equivalent for miRNA of interest
1263 at 0.05X concentration in 1X TE buffer. All serum miRNA will be normalized to the geometric
1264 mean of external (Spike-In Control *C. elegans* miR-39) and internal controls to allow for both
1265 technical and inter-individual normalization [101]. Geometric mean of controls will be used to
1266 correct for possible outlying values and abundance differences between the different controls
1267 [102].

1268
1269 All reverse transcription for mRNA and miRNA, and pre-amplification of serum miRNA will be
1270 conducted in a T100[™] Thermal Cycler (Bio-Rad, Hercules, CA or similar model). A
1271 StepOnePlus[™] real-time PCR system (Applied Biosystems) or similar model will be used to
1272 perform all mRNA and miRNA analysis. Fold changes will be calculated using the $\Delta\Delta C_T$
1273 threshold ($\Delta\Delta C_T$) method as described below in statistical analysis section.

1274 1275 **Bioinformatics Analysis**

1276 microRNA with significant changes in their expression will be uploaded to DNA Intelligent
1277 Analysis (DIANA)-miRPath 3.0 (Alexander Fleming Biological Sciences Research Center
1278 [BSRC], Athens, Greece; <http://diana.cslab.ece.ntua.gr>) to determine potential molecular
1279 pathways that these microRNA have previously been reported to regulate. Relevant Kyoto
1280 Encyclopedia of Genes and Genomes (KEGG; <http://www.genome.jp/kegg/>) pathways will be
1281 identified using experimentally verified targets from TarBase 7.0 (Alexander Fleming BSRC).
1282 Based on findings from this analysis, any additional gene and protein expression of relevant
1283 targets will be assessed.

1284 1285 **Western Blotting**

1286 Approximately 30 mg of muscle will be homogenized in ice-cold buffer (1:10 w/v) containing 50
1287 mM Tris-HCl (pH 7.5), 5 mM Na-pyrophosphate, 50 mM NaF, 1 mM EDTA, 1 mM EGTA, 10%
1288 glycerol (v/v), 1% Triton-X, 1 mM DTT, 1 mM benz-amidine, 1 mM PMSF, 10 μ g mL⁻¹ trypsin
1289 inhibitor and 2 μ g mL⁻¹ aprotinin. Homogenate will be centrifuged for 15 min at 10,000 \times g at
1290 4°C. Protein concentration of supernatant (lysate) will be determined using 660 nm Protein
1291 Assay (ThermoFisher Scientific, Waltham, MA, USA or equivalent). Phosphorylation status and
1292 total protein expression of intramuscular inflammation and markers of muscle carbohydrate
1293 metabolism will be determined by Western blot. Muscle lysates will be solubilized in Laemmli
1294 buffer, with equal amounts of total protein (15 μ g) separated by SDS-PAGE using precast
1295 Tris-HCl gels (Bio-Rad). Proteins will be transferred to polyvinylidene difluoride (PVDF)
1296 membranes and incubated with commercially available primary antibodies of intracellular
1297 markers involved in inflammation, anabolism, proteolysis, and substrate metabolism [e.g., IL-6,
1298 TNF α , NF- κ B, IKK α / β , Akt, mTORC1, p70S6, AMPK α , p38 MAPK, PGC-1 α , SIRT1, CaMK,
1299 p53, and ACC (Cell Signaling Technology, Danvers, MA, USA)] at 4°C overnight. Labeling will
1300 be performed using secondary antibody (anti-rabbit IgG conjugate with horseradish peroxidase;
1301 Cell Signaling Technology), and chemiluminescent reagent will be applied (Super Signal, West
1302 Pico Kit; Pierce Biotechnology, Rockford, IL, USA or equivalent). Blots will be quantified using
1303 the ChemiDoc XRS from Bio-Rad and Image Lab software (Bio-Rad) or similar model. To
1304 confirm equal protein loading per well a normalizing protein such as HSP90 or GAPDH will be
1305 assessed.

1306
1307
1308
1309
1310
1311
1312
1313
1314
1315
1316
1317
1318
1319
1320
1321
1322
1323
1324
1325
1326
1327
1328
1329
1330
1331
1332
1333
1334
1335
1336
1337
1338
1339
1340
1341
1342
1343
1344
1345
1346
1347
1348
1349
1350
1351
1352
1353
1354
1355

B5.5 Managing Data and/or Human Biological Specimens for this Research

All data and medical information obtained will be considered privileged and held in confidence. Study volunteers will be assigned unique subject identification (ID) numbers that will not contain any personal identifiers such as name, social security number, address, date of birth, zip code, etc. Subject ID numbers will be used on all data collection instruments, to include questionnaires, data collection forms, computer records, etc. A number will be assigned as each volunteer is enrolled for participation. A master list linking the volunteers' names and ID numbers will be kept in a separate locked file in the principal investigator's or the project coordinator's office, or kept in a computer file with password-protected access restricted to the principal investigator and the project coordinator. Social security numbers and banking information will be collected to process volunteer payments. The master list link, social security numbers, and banking information will be deleted immediately after the study has been completed and payment has been confirmed. When the results of the research are published or discussed in conferences, no information will be included that would reveal identity. Study biological samples will be processed on site at USARIEM and stored in Military Nutrition laboratory freezers (rooms 322, 304) using the subject identification number until analyzed on site or until sample aliquots are shipped to other laboratories for analysis. Aliquots will be made of all study samples and stored on site in Military Nutrition laboratory freezers indefinitely for reanalysis if necessary. Aliquots of coded biological samples will be shipped overnight on dry ice to [name] at USACEHER, [name] at PBRC, Metabolic Solutions Inc., and to the Energy and Environmental Sustainability Laboratory (EESL PSU) at Pennsylvania State University for analyses. Once samples have been analyzed by these respective laboratories, there will be no remaining sample for storage. Coded data will be transmitted between the abovementioned laboratories and USARIEM, as well as between USARIEM and the University of Leeds via encrypted email, a secure file transfer site, or using an approved removable media. Coded specimen/data transfer agreements have been obtained for PRB and University of Leeds. Further, USARIEM has existing collaborative agreements in place with the Norwegian Defence Research Establishment (CRADA W81XWH-12-0270) and the University of Leeds (W81XWH-16-0498). An institutional collaborative agreement is currently in review between USARIEM and USACEHR.

Only personnel assigned to the research study by the principal investigator will have access to the data. Only the principal investigator and project coordinator will have access to personal identifiable data. No outside laboratory will have access to identifiable data. Hard copy data records will be stored for a minimum of three years from the time the study is completed. Electronic data records will be maintained for a period of at least ten years after the study has been completed.

B5.6 Managing Data and/or Human Biological Specimens for Future Research

Any use of the samples outside of the broad scope of this protocol will be submitted as a protocol amendment or a new protocol. Once the protocol is closed, samples will be retained for further analyses that may or may not align with the hypotheses set forth in the protocol. Samples will be retained for future analyses once the protocol is closed.

B5.7 Devices, Drugs, Dietary Supplements, Nutritional Supplements, And Biologics

B5.7.1 Devices

1356
 1357
 1358
 1359
 1360
 1361
 1362
 1363
 1364
 1365
 1366
 1367
 1368
 1369
 1370
 1371
 1372
 1373
 1374
 1375
 1376
 1377
 1378
 1379
 1380
 1381
 1382
 1383
 1384
 1385
 1386
 1387
 1388
 1389
 1390
 1391
 1392
 1393
 1394
 1395

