434 approach will enable studying interactions among the microbiome and host physiology, the
435 “interactome”, to elucidate how the interactome responds to SUSOPS and the role of negative
436 energy balance in this response.

437

438 **B3. MILITARY RELEVANCE**

439 Warfighters are often exposed to physical and cognitive stress, which likely contribute to
440 documented declines in iron status, physical performance, and cognitive function during military
441 training [30, 31, 61]. Thus, it is critical to identify factors that contribute to the decline in iron
442 status and effective interventions to sustain and optimize Warfighter health and performance.
443 This highly-controlled study will delineate the effects of repeated bouts of strenuous activity
444 endured during SUSOPS on the IL-6 and hepcidin response, iron absorption and status, whole-
445 body and skeletal muscle homeostasis, physical and cognitive performance, and determine if

446 maintaining energy balance is an effective strategy to mitigate that response. Data obtained
447 from this study may be used in the development of countermeasures to attenuate the
448 detrimental physiological effects of negative energy balance during strenuous military
449 operations. Data obtained from this study will also be used to identify novel potential
450 biomarkers associated with the severity of stress responses to strenuous military operations.

451

452 **B4. OBJECTIVES/SPECIFIC AIMS/RESEARCH QUESTIONS**

453

454 **Objectives**

455

- 456 1. To determine the effects of a simulated 72-h SUSOPS on IL-6, hepcidin, and
457 fractional iron absorption.
- 458
- 459 2. To determine whether energy balance and severe energy deficit modulate IL-6,
460 hepcidin, and fractional iron absorption during a simulated 72-h SUSOPS.

461

462 **Secondary Objectives**

463

- 464 1. To determine whether energy balance and severe energy deficit modulate
465 intramuscular inflammation, transcriptional modifications (e.g., microRNA and factors
466 involved with energy substrate metabolism), anabolic signaling, remodeling, and
467 whole-body (e.g., protein balance, immune function, etc.) adaptive responses to a
468 simulated 72-h SUSOPS.
- 469
- 470 2. To determine to what extent maintaining energy balance mitigates decrements in
471 intestinal barrier integrity and in gut microbiome composition and function, and
472 influences gastrointestinal transit time during a simulated 72-h SUSOPS.
- 473

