518 dynamics and biological pathways within the human host that are affected by
519 military-relevant stress and are associated with physical and cognitive performance,
520 and identify novel markers of physiological stress.

521

522 **B5. RESEARCH PLAN**

523

524 **B5.1 Research Design**

525

526 This randomized cross-over study will consist of four sequential phases (SUSOPS 1, Recovery
527 1, SUSOPS 2, and Recovery 2).

528

529 **B5.2 Research Subjects/Population(s)**

530

531 **B5.2.1 Subject Population(s)**

532

533 Healthy, recreationally-active adult men, who are active duty military, will be recruited to
534 participate in this study. Male subjects were chosen because of known sex differences in
535 iron status and absorption and differences in their response to exercise, including the IL-
536 6 response to exercise [62, 63]. Pending the outcomes from this study, future, more
537 targeted studies will be designed to address potential sex-based differences in
538 physiological responses to SUSOPS.

539

540 **B5.2.2 Number of Subjects, Records, and/or Specimens**

541

542 This protocol requires 15 subjects complete testing to provide 80% power to detect
543 significant differences in circulating hepcidin responses between SUSOPS 1 and
544 SUSOPS 2. Up to 60 subjects will be enrolled to account for attrition and screening

545 failures in order to get complete data on 15 subjects. See section B5.8.1 for details on
546 sample size calculations.
547

548 **B5.2.3 Inclusion Criteria**

- 549 • Men who are active duty military, aged 18 – 39 years
- 550 • Weight stable in the past 2 months (\pm 2.27 kg)
- 551 • Healthy without evidence of chronic illness, medication use, or musculoskeletal injury
- 552 as determined by the USARIEM Office of Medical Support and Oversight (OMSO)
- 553 • Recreationally active (2-4 days per week aerobic and/or resistance exercise)
- 554 • Refrain from taking any pain-relievers (e.g., acetaminophen), nonsteroidal anti-
- 555 inflammatory drugs (e.g., aspirin, Advil®, Aleve®, Naprosyn®), or any other aspirin-
- 556 containing product for 10 days before starting and at least 5 days after completing
- 557 the study
- 558 • Refrain from the use of alcohol and nicotine for the duration of the study
- 559 • Willing to refrain from alcohol, smoking any nicotine product (includes e-cigarettes),
- 560 vaping, chewing tobacco, caffeine, and dietary supplement use, and from

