629 Fasted blood draws will be collected on days 7-9 during Recovery 1, and a second baseline
630 mood/cognitive test session will occur during Recovery 1. Starting on day 11, volunteers will
631 complete a second glycogen normalization and 48 h carbohydrate refeeding protocol. On day
632 13, following an overnight fast, a blood draw and a third muscle biopsy (alternate leg from
633 biopsy two) will be collected. Immediately thereafter, volunteers will complete the second 72 h
634 SUSOPS. All testing, planned activity, and sleep restrictions will be the same as described for
635 SUSOPS I; however, volunteers will switch to either SUSOPS BAL or SUSOPS NEG BAL. Iron
636 Study 3 ($^{58}\text{FeSO}_4$) and the fourth and final muscle biopsy (alternate leg from biopsy three) will
637 occur on day 16 immediately following the final exercise bout and 8 h after dinner on day 15.
638 Days 17-22 will serve as Recovery 2 (7 d post-SUSOPS recovery blood draw will be collected on
639 day 22 to match the 7 d recovery from SUSOPS 1) Diet records will be recorded on days 6-8,
640 and 16-18.

641

642 **SUSOPS BAL and SUSOPS NEG BAL**

643 The SUSOPS will be comprised of a variety of Warfighter tasks, designed to elicit high energy
644 expenditures, muscle damage and fatigue, sleep deprivation, and decrements in physical and
645 cognitive performance as well as self-reported mood status. Most importantly, the SUSOPS will
646 be designed to elicit a marked inflammatory response. Physical activity/exercise will be
647 prescribed at levels to expend ~ 5000 - 6000 total kcal/d using the ACSM metabolic equations for
648 steady-state exercise [64] and the compendium of metabolic equivalents for physical activities
649 [65]. Total daily energy expenditure estimates will be consistent with our recent reports in
650 Norwegian Soldiers and matched between SUSOPS BAL and NEG BAL [55, 66]. Combat
651 rations (Meal Ready-to-Eat) will serve as the underlying diet during SUSOPS BAL and NEG
652 BAL (refer to SUSOPS Diet Intervention section for details). Low-to-moderate intensity (30 - 65%
653 $\text{VO}_{2\text{peak}}$) steady-state endurance-type exercise will be the primary exercise modality.
654 Volunteers will perform three prolonged steady-state exercise bouts per day. All three exercise
655 sessions will be conducted outdoors on Natick Soldier Systems Center grounds (NSSC fitness
656 trail). Two of the three exercise bouts will be ~ 60 - 180 -min load carriage exercise sessions,

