1455 liberal false discovery rate (e.g., 0.20) may be used to reduce type 2 error rates and
1456 increase power. For microbiome analysis, shotgun sequencing (maximum 50 million
1457 pair end reads) of 15 participants will achieve $\geq 69\%$ power to detect a true difference in
1458 relative abundance of at least 1.5 fold with group coefficient variation 1.3, and false
1459 discovery rate of 0.05. Again, a more liberal false discovery rate (e.g., 0.20) may be
1460 used to reduce type 2 error rates and increase power. Power calculations were
1461 conducted using pairwise distances and PERMANOVA power with respect to effect size.
1462 However, power will be enhanced by correlating the blood mRNA data with other omics
1463 readouts derived from saliva (microRNA-seq, metabolomics and microbiome) and blood
1464 (targeted microRNA and metabolomics), and by temporal sample collection. As such,
1465 we expect that 15 participants will provide adequate power to detect differences in blood
1466 mRNA expression, and gut microbiome community and genome composition between
1467 study phases, and correlations between these parameters and other –omics readouts.

1468 **B5.8.2 Data analysis**

1469
1470
1471 Statistical analyses will be conducted using either SPSS (IBM Corp. Armonk, NY), SAS
1472 9.3 (SAS Institute Inc., Cary, NC), or equivalent. Common descriptive statistics will be
1473 used to describe volunteer characteristics. Shapiro-Wilk tests will be used to determine
1474 normality of data, and transformations will be applied as appropriate to ensure model
1475 assumptions are met. Correlation and multiple regression will be used to evaluate
1476 relationships between study outcomes.

1477 **Primary Objectives**

1478
1479 Linear mixed models will be used to determine main effects of phase (SUSOPS BAL and
1480 SUSOPS NEG BAL), time within phase, and their interaction on inflammation, iron
1481 absorption, mood/cognitive, and measures of muscle, nutritional, and metabolic
1482 homeostasis. If phase by time interactions are observed, a Bonferroni correction will be
1483 applied for multiple comparisons. Statistical significance will be set at $P < 0.05$. To test
1484 for carryover effects a main effect of group (SUSOPS BAL first, SUSOPS NEG BAL first)

1485 and a group-by-phase interaction will be included in initial models. These terms will be
1486 removed if they do not significantly contribute to the overall fit of the model. When

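### B5.2.2 states the 80% hepcidin power for SUSOPS 1 versus SUSOPS 2 rather than for BAL versus NEG BAL, and its 15 completers do not agree with the 11 in B5.8.1

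*Combined protocol and SAP*

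**What the plan says.** Section B5.2.2 reads: "This protocol requires 15 subjects complete testing to provide 80% power to detect" "significant differences in circulating hepcidin responses between SUSOPS 1 and" SUSOPS 2. It allows up to 60 enrolments so that 15 men have complete data, and refers to B5.8.1 for the calculation.

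Section B5.1 defines the labels: "This randomized cross-over study will consist of four sequential phases", of which SUSOPS 1 is the first and SUSOPS 2 the third. Under Experimental Design in B5.3, the first SUSOPS is run on either diet, and for the second "volunteers will switch to either SUSOPS BAL or SUSOPS NEG BAL". B5.8.2 confirms two sequences: "group (SUSOPS BAL first, SUSOPS NEG BAL first").

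The question asked is about diet. Objective 2 in B4 begins "To determine whether energy balance and severe energy deficit modulate IL-6" and goes on to hepcidin and fractional iron absorption. For the primary objectives, B5.8.2 says "Linear mixed models will be used to determine main effects of phase (SUSOPS BAL and" SUSOPS NEG BAL), with time within phase and the interaction. So phase means a stretch of calendar time in B5.1 and a diet condition in B5.8.2.

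B5.8.1 describes the power differently from B5.2.2. It says 11 participants suffice at alpha 0.05 and power 0.8 for changes in IL-6 and hepcidin in response to stress and to differences in energy balance, then adds 4 for attrition to make 15. Its inputs come from earlier studies in male athletes that found increases after exercise or training.

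**The concern.** The B5.2.2 sentence is the plan's short statement of why the trial has its size. It is also the only one that names hepcidin together with a comparison between the two SUSOPS.

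Read as written, it names the period contrast. No objective or hypothesis asks about period, and the primary model tests diet. Within one man the two contrasts are the same pair of measurements, but across the trial they differ: SUSOPS 1 minus SUSOPS 2 is BAL minus NEG BAL in one sequence and NEG BAL minus BAL in the other.

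Two further problems come with the wording. The same 80% is attached to 15 completers in B5.2.2 and to 11 participants in B5.8.1. And once the contrast is named correctly, it becomes clear that the inputs behind the calculation are not diet differences. A reader of the protocol or the eventual report could take 80% power for the diet effect on hepcidin as established when it has not been.

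**Working it through.** **Inputs (B5.8.1 table).** Hepcidin after a 7-day training block: mean difference 4.7, SD of difference 4.9, n 11. Hepcidin after a 1.5 h treadmill run: 7, SD 7.4, n 11. Alpha is 0.05. Sidedness is not stated; two-sided is assumed because it reproduces the table's hepcidin figures (one-sided gives 9).

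**Formula.** Paired t-test: standardised difference d = mean / SD, noncentrality = d × √n, power from the noncentral t distribution with n − 1 degrees of freedom.

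**Step 1: reproduce the plan's 11.**
- 4.7 / 4.9 = 0.959; × √11 = 3.18; power 0.817. At n = 10 it is 0.770, so 11 is the smallest n reaching 0.80.
- 7 / 7.4 = 0.946; × √11 = 3.14; power 0.807. At n = 10 it is 0.759.

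B5.8.1 reproduces exactly on both hepcidin rows.

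**Step 2: apply the same inputs at 15.**
- 0.959 × √15 = 3.71; power 0.932.
- 0.946 × √15 = 3.66; power 0.925.

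So 80% at 15 completers does not follow from the calculation that B5.2.2 cites. With 15 completers, 80% power corresponds to d of about 0.78, which appears in neither hepcidin row. The 15 is 11 + 4, an attrition allowance that B5.2.2 treats as the required number of completers.

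**Step 3: a period-adjusted diet test.** With 4.7/4.9 or 7/7.4 assumed as the diet difference and an assumed 8:7 split between sequences (the allocation ratio is not stated), simulated power at 15 is 0.93 and 0.92. Adjusting for period therefore costs little.

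**Step 4: power for the diet contrast under stated assumptions.** The documents give no BAL minus NEG BAL difference for hepcidin. Two quantities must be assumed: the fraction of 4.7 that the diet difference represents, and its SD. The larger SD is 4.9 × √2 = 6.93, which applies if the contrast is a difference between two uncorrelated changes, each with SD 4.9. Paired t-test, n = 15:

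| Assumed diet difference | SD 4.9 | SD 6.93 |
|---|---|---|
| 4.70 (100%) | 93% | 69% |
| 3.53 (75%) | 74% | 45% |
| 2.35 (50%) | 41% | 23% |

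The 7/7.4 inputs give nearly the same: 93%, 72% and 40% with SD 7.4, and 67%, 44% and 23% with the SD larger by √2.

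**The case against.** The strongest reply is that this is a slip of labels which the rest of the protocol resolves. B5.2.2 sends the reader to B5.8.1, which names energy balance. Objective 2, Hypothesis 2 and the B5.8.2 model all specify BAL and NEG BAL. The diet prescription section itself uses SUSOPS 1 and 2 loosely for the two diets when it explains how iron intake will be matched. All of this stands: the planned analysis is not affected, and correcting the label does not by itself change the sample size.

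A reader might go further and infer that the trial has almost no power. If the diet effect is taken as 4.7 with no period effect, an unadjusted paired test of SUSOPS 1 against SUSOPS 2 would reject only about 1% of the time at an assumed 8:7 split. The documents do not support that inference. The plan proposes no such test. Its initial models carry group and group-by-phase terms, and with phase coded as diet the group-by-phase term is the period contrast, estimated with diet in the model. With no period effect, a rejection rate for a period test is essentially a false-positive rate, not the power of the trial.

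What the objection does not remove is the mismatch of 15 with 11, or the absence of any diet difference among the inputs.

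**Conclusion.** The point holds as a fault in the power statement, not in the design or the analysis. B5.2.2 names the period contrast where the objective and model concern diet. Its pairing of 80% with 15 completers contradicts B5.8.1, whose inputs give about 81-82% at 11 and about 93% at 15 (two-sided paired t-test, alpha 0.05).

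Power for BAL versus NEG BAL on hepcidin has not been shown. At 15 completers it runs from about 93% down to about 23% over the assumed range above. Nor does this show that the trial is underpowered: the documents give no diet difference from which that could be judged.

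**What to change.** In B5.2.2, replace SUSOPS 1 and SUSOPS 2 with SUSOPS BAL and SUSOPS NEG BAL as the contrast that is powered.

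Reconcile B5.2.2 with B5.8.1. State whether 11 or 15 is the required number of completers, and whether attrition is covered by the 4 added men or by the enrolment ceiling of 60.

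Restate power at 15 for the diet contrast under the test that will be used. Give the assumed difference and SD, label both as assumptions, and say that the B5.8.1 inputs are increases after exercise or training. The table above can serve as the sensitivity range.

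The cost is one reworded sentence, one restated figure and a short note on assumptions. Randomisation, data collection and the model stay as they are.
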